#### Efficacy and safety

As an additional primary analysis, subject and graft survival at 6 months will be determined within each group. GFR measured at baseline and months 1, 3, 6, and 12 months will be descriptively summarized. Cumulative rates of acute and chronic rejection, and chronic allograft nephropathy, will be summarized, as well as incidence of post-transplant diabetes.

All AEs and SAEs since transplantation will be summarized for the patients receiving belatacept. For the control patients, rates of rejection, PTLD, and death will be summarized.

**5 SUBJECT SELECTION CRITERIA** 

For entry into the study, all subjects must meet the following criteria.

5.1 Inclusion Criteria Signed Written Informed Consent

1) The subject is willing to provide signed written informed consent

**Target Population** 

2) The subject is a first-time recipient of a living or deceased donor kidney transplant3) Evidence of calcineurin inhibitor side effects during the first 3 months after transplant as defined as

- 1. Neurologic toxicity, defined as tremor, altered mental status, or seizure
- 2. Renal toxicity, defined as GFR <60
- 3. Metabolic toxicity, defined as a new requirement for medication to control hyperglycemia
- 4. Hematologic toxicity, defined as development of thrombotic microangiopathy

#### Age and Gender

4) Men and women, ages 18 and older, inclusive

5) Women of childbearing potential (WOCBP) must be using an adequate method of contraception to avoid pregnancy throughout the study and for up to 8 weeks after the study in such a manner that the risk of pregnancy is minimized. See section 9.7 below for details regarding handling of WOCBP subjects.

WOCBP includes any female who has experienced menarche and who has not undergone successful surgical sterilization (hysterectomy, bilateral tubal ligation, or bilateral oophorectomy) or is not postmenopausal (defined as amenorrhea  $\geq 12$  consecutive months; or women on hormone replacement therapy with documented serum follicle stimulating hormone level > 35 mIU/mL). Even women who are using oral, implanted, or injectable contraceptive hormones or mechanical products such as an intrauterine device or barrier methods (diaphragm, condoms, spermicides) to prevent pregnancy or practicing abstinence or where the partner is sterile (e.g., vasectomy), should be considered to be of child bearing potential. WOCBP who are taking MMF must in addition use methods of birth control as stipulated in the package insert, namely:

Either intrauterine device, or partner with vasectomy, or one hormone (oral contraceptive pill, transdermal patch, vaginal ring, or progesterone injection or implant) and one barrier method (diaphragm or cervical cap with spermicide, contraceptive sponge, or male or female condom), or two barrier methods as described above.

WOCBP must have a negative serum pregnancy test (minimum sensitivity 25 IU/L or equivalent units of human chorionic gonadotropin [HCG]) within 72 hours prior to the start of study medication then every 3 months during the period of study participation.

6) Men must use an adequate method of contraception throughout the study, and for up to 8 weeks after the last infusion, so that the risk of pregnancy to their partners is minimized.

7) MMF must be dosed at 500 mg by mouth twice daily or greater at the time of study entry

8) Prednisone must be dosed at >=10 mg by mouth daily for patients less than 6 weeks posttransplantation, and at >=5mg by mouth daily for patients greater than 6 weeks posttransplantation at the time of study entry.

5.2 Exclusion Criteria Gender and Reproductive Status

1) WOCBP who are unwilling or unable to use an acceptable method to avoid pregnancy for the entire study period and for up to 8 weeks after the last infusion.

2) Women who are pregnant or breastfeeding

3) Women with a positive pregnancy test on enrollment or prior to study drug administration

4) Males unwilling or unable to use an adequate method of contraception for the entire study period and for up to 8 weeks after the last infusion of study medication

Immunologic status

5) Subjects with PRA  $\ge$  30% at time of transplant

6) Subjects with zero HLA antigen mismatched donors (either from related or unrelated donor)

7) Subjects with any prior solid organ transplant (including kidney)

8) Subjects receiving a concurrent solid organ (heart, liver, pancreas) or cell (islet, bone marrow, stem cell) transplant

9) Subjects with a history of biopsy-proven acute rejection post-transplant (humoral or cellular) in the first three months post transplantation

Infection related risks

10) Subjects who are hepatitis C antibody-positive or polymerase chain reaction

(PCR)-positive for hepatitis C

11) Subjects who are hepatitis B surface antigen-positive or PCR-positive for hepatitis B

12) Subjects with known human immunodeficiency virus (HIV) infection

13) Subjects with active tuberculosis (TB) requiring treatment within the previous 3 years or any subject who previously required triple (or more) combination therapy for TB.

14) Subjects who are EBV antibody negative and have received grafts from EBV antibody positive donors.

Prohibited Therapies and/or Medications

15) Subjects who have used any investigational drug within 30 days prior to the Day 1 visit

16) Subjects previously treated with belatacept

18) Use of mTOR inhibitors at any time after transplantation

Other Exclusion Criteria

18) Prisoners or subjects who are compulsorily detained (involuntarily incarcerated) for treatment of either a psychiatric or physical (e.g., infectious disease) illness must not be enrolled into this study.

19) Subjects who have difficult i.v. access or other reasons that would likely preclude medication administration

#### **6 STUDY CONDUCT**

#### 6.1 Ethics

This study will be conducted in accordance with the ethical principles that have their origin in the current Declaration of Helsinki, and will be consistent with International Conference on Harmonization Good Clinical Practice (ICH GCP) and applicable regulatory requirements.

The study will be conducted in compliance with the protocol. The protocol and any amendments and the subject informed consent will receive Institutional Review Board (IRB) approval prior to initiation of the study.

Freely given written informed consent must be obtained from every subject or their legally acceptable representative prior to clinical trial participation, including informed consent for any screening procedures conducted to establish subject eligibility for the trial.

For further details on informed consent, see Section 10.2.

The rights, safety and well-being of the trial subjects are the most important considerations and should prevail over interests of science and society.

Study personnel involved in conducting this trial will be qualified by education, training, and experience to perform their respective task(s).

This trial will not use the services of study personnel where sanctions have been invoked or where there has been scientific misconduct or fraud (e.g., loss of medical licensure, debarment).

Systems with procedures that assure the quality of every aspect of the study will be implemented.

#### 6.2 Study Therapy

#### 6.2.1 Treatment and Subject Identification

Study subjects will be switched to belatacept using the regimen described above. These treatments will be administered with concurrent maintenance therapy with MMF and corticosteroids. At the time of switch to belatacept, ongoing CNI therapy will be tapered to off over a 30 day course, as follows: 100% on day 1, 40-60% on day 15, 20-30% on day 23, and none on day 29 and beyond, following the previously published protocol[10]. An exception to this taper schedule would be made in the case of CNI toxicity with thrombotic microangiopathy, where tapering may be done over a two week time course.

MMF dosing will be maintained at a minimum of 500 mg by mouth twice daily.

For patients less than 6 weeks post-transplantation, prednisone dosing must be 10mg by mouth daily at the time of study entry and can be tapered to 5mg by mouth daily after 6 weeks post-transplantation. For patients who are greater than 6 weeks post-transplantation, prednisone must be at a minimum of 5mg by mouth daily and will be maintained at this level throughout the duration of the study.

At the time of enrollment, immediately after written informed consent is obtained and

before performing any study-related procedures, each subject will be assigned a unique sequential subject number for identification throughout the study. This subject number must not be reused for any other participant for the study.

#### 6.2.2 Administration of Belatacept

Day 1 is defined as the day of study drug administration (screening is Day 0). Infusion doses will be based on the subject's actual body weight at study Day 1, and will not be modified during the course of the study, unless there is a change of body weight ± 10% (see

Section 8.3.1). Study drug should be administered to the subject at a relatively constant rate over 30 minutes. See Section 8.3.1 for details on the preparation and administration of the study medication. See Section 7.2.6 for details on infusion visits and visit windows.

On study visit days, when the subject is to have peripheral blood collected, these measures are to be completed prior to belatacept dosing.

#### Belatacept Regimen

Subjects will receive intravenous belatacept at 5mg/kg every other week starting from day 1 and continuing with weeks 2, 4, 6, and 8, and then monthly at months 3, 4, 5, and 6. At month 6 patients may elect to continue for an additional six-month period of belatacept administration.

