Test Product, Dose and Mode of Administration, Duration of Treatment: Study patients will receive intravenous belatacept at 5mg/kg every two weeks at day 1 and weeks 2, 4, 6, and 8, and then monthly at months 3, 4, and 5. At month 6 patients may elect to continue for an additional six month period of belatacept administration. Peripheral blood mononuclear cells (PBMCs) and sera for antibody testing will be collected at time of study entry and at 4, 8, 12, and 24 weeks after belatacept start, frozen and banked at our center, and analyzed in batch fashion for development of humoral and cell mediated immunity. Patients who elect to receive an additional 6 months of belatacept treatment will undergo additional immunologic analysis at 1 year after study entry.

Reference Therapy, Dose and Mode of Administration, Duration of Treatment: Immunologic evaluations performed on study patients will be compared with a matched group of 20

control patients receiving conventional immunosuppressive therapy and participating in an ongoing observational trial regarding immunologic mechanisms contributing to rejection in kidney transplant patients.

Criteria for Evaluation:

Primary Outcome Measures:

- Donor specific antibody testing at Month 6
- Cell surface cytokine secretion in response to donor cell antigen by direct and indirect stimulation at Month 6
- Cell surface cytokine secretion in response to CMV and EBV antigens by direct and indirect stimulation at Month 6
- Immunophenotyping to determine overall immune profile at Month 6
- Patient and functional graft survival in stable renal transplant recipients

Secondary Outcome Measures:

- Donor specific antibody testing at Months 1 and 3 (and month 12 if continuing in study)
- Cell surface cytokine secretion in response to donor cell antigen by direct and indirect stimulation at Months 1 and 3 (and month 12 if continuing in study)
- Cell surface cytokine secretion in response to CMV and EBV antigens by direct and indirect stimulation at Months 1 and 3 (and month 12 if continuing in study)

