7.2.3 Infusion-only Visit Procedures

a) To occur on Days 1 as above, as well as weeks 2, 6, 8, 16, and 20

- b) Obtain weight and vital signs
- c) Review for changes in concomitant medication and AEs
- d) Administer study medication

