#### 7.2.4 Standard Study Visits

a) To occur on Weeks 4, 12, and 24 as well as week 48 for those electing to continue in the study

- b) Assess and record AEs pretreatment.
- c) Check and record any changes in concomitant medications
- d) Obtain weight and vital signs

e) Draw whole blood for immunology analysis, to be sent by courier to the Immunogenetics Center

- f) DSA testing
- g) EBV PCR testing

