### h) WOCBP will undergo pregnancy testing at weeks 12 and 24 as well as week 48 for those continuing in the study

i) Administer study medication

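### For subjects who decline the extension, the protocol both includes and omits a belatacept infusion at month 6 (8 versus 9 planned infusions)

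*Combined protocol and SAP*

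**What the plan says.** Four places in the protocol set out the infusion times in the first six months.

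- **Synopsis (test product paragraph) and 3.1.2 Overview:** 5 mg/kg "at day 1 and weeks 2, 4, 6, and 8, and then monthly at months 3, 4, and 5".
- **6.2.2, Belatacept Regimen:** day 1 and the same two-weekly times, "and then monthly at months 3, 4, 5, and 6". The next sentence reads "At month 6 patients may elect to continue for an additional six-month period of belatacept administration". It does not make the month-6 infusion depend on that choice.
- **7.2.3 Infusion-only visits:** "To occur on Days 1 as above, as well as weeks 2, 6, 8, 16, and 20".
- **7.2.4 Standard study visits:** "To occur on Weeks 4, 12, and 24 as well as week 48 for those electing to continue in the study". The list of procedures for these visits ends with "Administer study medication". Only week 48 is limited to subjects who continue.

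Three other passages touch the schedule without settling it. Section 1.3 gives five two-weekly doses and then monthly dosing, with no end month. Section 6.2.1 refers back to the regimen already described, which leads to 3.1.2. The dose windows in 7.2.6 run to month 6.

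**The concern.** The synopsis and 3.1.2 stop at month 5. Section 6.2.2, where site staff would look for the regimen, goes on to month 6. Section 3.1.1 leaves the extension to the patient's preference, so some subjects may stop at month 6. For them the protocol gives two answers on whether study drug is infused at the week-24 visit.

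What is at stake is conduct rather than inference. Section 6.2.5 requires medication to be given as the protocol describes and deviations to be documented, and 10.1 restricts unapproved deviations. Whatever is done at week 24 for a subject who stops departs from one section. The choice also fixes planned exposure and the date of the last infusion. The contraception periods for men (5.1, 5.2) and women (5.2, 9.7) and the live-vaccine interval (6.4.2.1) are counted from that date.

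**Working it through.** **Inputs.** Infusion times are those listed above. The dose is 5 mg/kg and there are 20 belatacept subjects (synopsis; 3.1.2). Months 3, 4, 5 and 6 are taken as weeks 12, 16, 20 and 24, which is how the visit lists space them.

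**Check against the one count the protocol states.** Day 1 and weeks 2, 4, 6, 8 make 5 infusions, which agrees with the five two-weekly doses in 1.3. No total number of infusions is stated anywhere.

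**Count by source, first six months.**

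| Source | Infusions | Total | Last |
|---|---|---|---|
| Synopsis, 3.1.2 | 5 + 3 (months 3, 4, 5) | 8 | week 20 |
| 6.2.2 | 5 + 4 (months 3, 4, 5, 6) | 9 | week 24 |
| 7.2.3 plus 7.2.4 | 6 (day 1; weeks 2, 6, 8, 16, 20) + 3 (weeks 4, 12, 24) | 9 | week 24 |

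The visit lists, put in order, give exactly the times in 6.2.2. The only time on which the sources differ is week 24.

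**Size for one subject who does not continue.**

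- Planned exposure: 8 × 5 = 40 mg/kg versus 9 × 5 = 45 mg/kg; 45/40 − 1 = 12.5%.
- Last infusion: week 20 versus week 24, a difference of 4 weeks.
- Eight weeks after the last infusion: 20 + 8 = week 28 versus 24 + 8 = week 32.
- Three-month live-vaccine minimum: 5 + 3 = month 8 versus 6 + 3 = month 9.

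**Size across the trial.** If k subjects decline the extension, the schedules differ by k infusions among them, with k between 0 and 20. The documents give no expected k. At the upper limit, where nobody extends, the totals are 20 × 8 = 160 and 20 × 9 = 180.

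**Does it reach the month-6 endpoints?** Sections 6.2.2, 7.3 and 7.3.4 place sampling before dosing. The week-24 sample therefore precedes any infusion that day, and both schedules are identical up to that point.

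**The case against.** The best defence is that month 6 is the first extension infusion: the synopsis and 3.1.2 list the core course, and 6.2.2 simply runs on by one. For subjects who continue, this reading works and removes the conflict. A reader might infer that no subject can be treated in line with both versions, or that all 20 are affected. The documents do not support either inference, because the 8-versus-9 contrast and the shift in last infusion describe only those who stop. For them the defence fails: 6.2.2 lists month 6 for subjects generally and mentions the choice to continue only afterwards, without linking the two.

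The visit lists are also weaker evidence than their exact match suggests. The dosing line in 7.2.4 is one generic item covering weeks 4, 12, 24 and 48. Read literally, it also doses at week 48, the end of the extension, and neither list shows any extension infusion between weeks 24 and 48. They may reflect a shared visit template. That objection stands, so the lists are supporting evidence only. The direct contradiction is the synopsis and 3.1.2 against 6.2.2.

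The drug-infusion row of the procedures table is damaged in the text available here, and the schedule figure in 7.1, which marks infusions, is not shown. Both could bear on week 24, and neither is used for or against the point. They could not remove the conflict between the prose sections.

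Finally, periods counted from the last infusion can be applied under either schedule: they follow the infusion actually given, and only the calendar date moves. The contraception inclusion criterion for women in 5.1 counts from the end of the study and does not move for this reason.

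**Conclusion.** The contradiction is real, narrow and visible in intact text. For subjects who do not elect the extension (number unknown, at most 20), the protocol both includes and omits an infusion at week 24. Per subject that is 8 versus 9 infusions, 40 versus 45 mg/kg, and a last infusion at week 20 versus week 24. The figures assume that every scheduled infusion is given at 5 mg/kg and that months map to weeks as in the visit lists.

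A reader might go further and infer an effect on the trial's results. The documents do not show one. The month-6 immunologic comparison is protected by pre-dose sampling. Month-12 immunologic sampling applies only to subjects who continue, for whom the conflict need not arise. The 12-month post-transplant survival and rejection outcome could include subjects who stopped, but no effect on it is demonstrated. The safety summary in 4.2 is descriptive, with no exposure-adjusted analysis, so no effect there is shown either.

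The reason to correct it is that a study-drug instruction should not have two answers. This point takes no position on which schedule is right.

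**What to change.** Reconcile the synopsis, 3.1.2, 6.2.2, 7.2.3 and 7.2.4 to a single infusion list. State explicitly whether week 24 is an infusion visit for subjects who do not continue, and word the dosing item in 7.2.4 so that it says to which visits and which subjects it applies. Check that the procedures table and the schedule figure in the full document agree with that list. The sponsor and investigator must decide which schedule applies.

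The cost is one wording amendment with the usual review. Sample size, endpoints and analyses do not change.

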#### 6.2.3 Dose Modifications

In the absence of AEs deemed at least possibly related to study drug treatment, subjects will complete their scheduled infusions as prescribed by protocol. In the event of new, serious, and unexpected toxicity potentially related to belatacept, study drug administration should be interrupted..

#### 6.2.4 Discontinuation of Therapy

Study therapy MUST be immediately discontinued for the following reasons:

- Withdrawal of informed consent (subject's decision to withdraw for any reason)
- Any clinical AE, laboratory abnormality, or intercurrent illness which, in the opinion of the investigator, indicates that continued treatment with study therapy is not in the best interest of the subject
- Pregnancy

• Imprisonment or the compulsory detention for treatment of either a psychiatric or physical illness (e.g., infectious disease).

#### 6.2.5 Treatment Compliance

All medications specified in this protocol must be administered as described within the

protocol. Study medication usage is to be reviewed, and compliance is to be discussed with subjects at each visit to assure compliance. All study medication and concomitant medication usage will be collected, and any deviations from specified administration should be clearly documented.

6.2.6 Other Guidance: Prior and Concomitant Therapy6.2.6.1 CorticosteroidsAll subjects in this study will be treated with daily corticosteroids.

6.2.6.2 Mycophenolate Mofetil

All subjects in this study will be treated with MMF. Daily MMF should be administered in 2 divided doses on a consistent schedule in relation to time of day and meals.

6.2.6.3 Basiliximab Dosing

Basiliximab dosing is up to the discretion of the treating physician using common practice at the study institution, typically given at two doses of 20 mg each.

6.2.6.4 Prophylaxis medications

Medications commonly in use for antibiotic prophylaxis will be continued following normal transplant protocols in place at our center. These medications include sulfamethoxazole/trimethoprim and valganciclovir or acyclovir. To summarize, patients who are antibody negative for CMV (R-) receiving transplants from CMV antibody positive donors (D+) will receive valganciclovir prophylaxis for the first 6 months post transplant at 900 mg daily by mouth, or as adjusted for their renal function. Patients with other CMV serology combinations (D-/R-, D+/R+, and D-/R+) will receive acyclovir 400 mg daily by mouth for the first 3 months post transplant. In addition, single-strength trimethoprim-sulfamethoxazole is given daily by mouth for the first 3 months post transplant.

6.2.6.5 Diagnosis and Treatment of Rejection

Screening for acute and chronic rejection will be performed using standard protocols in place at our center. Biopsy performance will be per center standard protocols. Treatment will be up to the discretion of the treating transplant nephrologist. The severity of acute rejection will be determined using the Banff 97 classification. Full Banff subscores will be obtained and reported.

6.3 Blinding/Unblinding

As this is an open label study, no arrangements need to be made for blinding or potential unblinding.

6.4 Prohibited and Restricted Therapies During the Study6.4.1 Prohibited TherapiesNo prohibited therapies.

#### 6.4.2 Precautions

#### 6.4.2.1 Vaccinations

There is limited information available regarding the effectiveness of immunizations in non-human primates and humans that have been treated with belatacept. No data are available on the effect of therapeutic vaccinations in subjects receiving belatacept.

Due to the risk of infection, vaccination of subjects with any live vaccine is absolutely contraindicated during the course of the study, as is the administration of LIVE oral polio vaccine to household contacts. The Centers for Disease Control recommend that subjects should not be administered a live virus vaccination for at least 3 months after discontinuing high dose corticosteroid therapy (defined as > 20 mg/day of prednisone for > 2 weeks). In view of the long half-life of belatacept, study subjects should not be administered a live virus vaccine for a minimum of 3 months following the last dose of study medication.

